9.2 Statistical Hypotheses

We hypothesize that treatment with high dose oxytocin nasal spray will result in a large effect size as measured by partial eta squared for the difference in mean area under the curve in baseline adjusted VAS when compared to placebo during the blinded study phase.

The primary outcome measurement will be the collective area under the VAS curve above the week 3 baseline as assessed from week 3 to week 6 of the blinded study phase. The area under the curve will be determined using the linear trapezoidal method for each participant after subtracting the baseline (week 3) VAS value from each subsequent measure to determine the collective improvement/decline of the VAS measurement during the blinded study phase. The mean and standard deviation of the total area will be

calculated for each study arm (active drug and placebo) and partial eta squared effect size for the difference determined. This effect size estimate can then be used to power future comparative studies.

The same area under the curve above the baseline VAS metric will be determined separately for the nonblinded/open label study phase. The inherent bias of non-blinding may influence this metric although the relatively larger sample size (n=30) could also improve precision. Therefore, the area will be presented as a descriptive summary using the mean and standard deviation with an effect size estimate.

Secondary endpoints will consist of safety and tolerability metrics including adverse event incidence and severity, regimen adherence and voluntary study drop-out rates reported during the non-blinded and blinded study phases. The frequency and percentage of each secondary measure will be determined for the non-blinded study phase and by study arm for blinded study phase. Additionally, any changes in THI greater than 1 grade will be determined from week 3 to week 6 of the blinded study phase. The frequency and percentage of these changes will be summarized by study arm.

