- 3. A 6 week double-blinded phase in which half of the participants will receive oxytocin nasal spray and half will receive placebo nasal spray. Neither the PI nor subject will know which drug they are receiving. However, the study coordinator will have access to this information as required to assign the medications.

Patients will come to the Preston Robert Tisch Center for Men's Health for study visits every 2 weeks and be administered the VAS and THI/CGI scales by the research coordinator or principal investigator. The screening visit will be the most comprehensive and include obtaining informed consent, a physical exam with vital signs, laboratory studies, questionnaires, an ECG, and review of medical and medication history to confirm all inclusion criteria are met and that there are no exclusion criteria present. During these visits they will have urine testing for sodium and osmolality. Every other week, they will receive a phone call from study staff to discuss their experience using the study drug and monitor for any adverse effects. They will complete the Tinnitus Functional Index questionnaire over the phone as well. When the subjects come in for their study visit, 4 weeks after the baseline period, they will receive enough study medication for the rest of the study, to allow for randomization to placebo or active drug at that time.

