5.6 Total Number of Participants and Sites

Recruitment will end when approximately 50 participants are enrolled. It is expected that approximately 50 participants will be enrolled in order to produce 30 evaluable participants. These participants between the ages of 18 and 75 are to be entered into this study at NYU Langone Medical Center. This research project will only be taking place at this site. This study will be an out-patient study. The study visits will be at the NYU Langone Preston Robert Tisch Center for Men's Health, [name].

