9.5 Sample Size

This is a pilot, proof of concept study with the main goal of providing an estimate of the effect size difference between treatment and placebo control. As such the sample size of n=30 will provide sufficient estimates of the effect sizes necessary to power a future two-armed randomized study

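### Partial eta squared, the planned basis for powering later trials, is biased upward at 15 per arm, unsigned and reported without an interval; imprecision is the larger problem

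*Combined protocol and SAP*

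**What the plan says.** Section 9.2 defines the primary outcome as the area under the baseline-subtracted VAS curve in the blinded phase. The mean and SD of that area are to be computed by arm, and the "partial eta squared effect size for the difference determined. This effect size estimate can then be used to power future comparative studies". The hypothesis is that oxytocin "will result in a large effect size as measured by partial eta squared". Sections 9.1 and 9.4.2 set small, medium and large at 0.2, 0.5 and 0.8 on the eta squared scale, and 9.4.2 counts 0.5 or more as a treatment success.

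Section 9.5 gives the "main goal of providing an estimate of the effect size difference between treatment and placebo control" as the purpose of the study and rests the sample size on it: "As such the sample size of n=30 will provide sufficient estimates of the effect sizes necessary to power a future two-armed randomized study". No formula, precision target, alpha or power accompanies that sentence.

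On numbers, Section 4.1 says that "half of the participants will receive oxytocin nasal spray and half will receive placebo nasal spray", and Section 5.6 expects that "50 participants will be enrolled in order to produce 30 evaluable participants". Together these give 15 per arm, as Section 3 also states.

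No section plans a bias-corrected index, a confidence interval for the effect size, or a cautious planning value.

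**The concern.** Sample eta squared is a ratio of sums of squares. It cannot fall below zero, so chance differences between arms always push it up. The effect is largest where the sample is small and the true effect modest. It also discards direction: a pilot favouring placebo gives the same value as one favouring oxytocin.

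The index is the study's main product and the only planning quantity that the plan names. If a later team sizes a trial from the raw value, that trial may miss its intended power, and without an interval nothing in the effect-size output shows how uncertain the value is.

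**Working it through.** **Inputs from the documents.** N = 30, allocation 1:1, 15 per arm (4.1, 5.6, 9.5). No covariate is named for the comparison, so partial eta squared equals plain eta squared (η²).

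**Assumptions.** The documents do not state the true effect or the design of the next trial. I use true η² from 0.010 to 0.8, and a two-arm trial at two-sided 0.05 with 80% power.

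**Nothing to reproduce.** The figure n = 30 has no stated derivation.

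**Formulas.**
- Effect size: η² = d²/(d² + 4), so d = 2√(η²/(1 − η²)). Thus d = 0.2, 0.5, 0.8 correspond to η² = 0.010, 0.059, 0.138. The plan's 0.2, 0.5, 0.8 on the η² scale correspond to d = 1, 2, 4.
- Sampling distribution: observed η² = F/(F + 28), with F noncentral on 1 and 28 df and λ = 30η²/(1 − η²).
- Expected value with no effect: 1/(N − 1) = 1/29 = 0.034.
- Planned n per arm: 2(1.960 + 0.842)²/d² = 3.92(1 − η²)/η², rounded up. For η² = 0.059 this is 3.92 × 16 = 62.8, so 63.

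**Results, 1,000,000 simulated pilots per row.** Each pilot's own η² goes into the sample-size formula. The planned n is compared with the n that the true effect needs.

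| True η² (d) | Mean observed η² | n/arm needed | Median n/arm planned | Undersized | Over twice the need | Average achieved power |
|---|---|---|---|---|---|---|
| 0.010 (0.2) | 0.044 | 389 | about 175 | 65% | 25% | 54% |
| 0.059 (0.5) | 0.090 | 63 | 57 | 52% | 32% | 70% |
| 0.138 (0.8) | 0.165 | 25 | 23 | 53% | 24% | 74% |
| 0.20 (1.0) | 0.224 | 16 | 15 | 52% | 19% | 75% |
| 0.50 (2.0) | 0.517 | 4 | 4 | 34% | 5% | 80% |

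At a true 0.8 the mean observed value is 0.810 (+1%). With 24 evaluable instead of 30 (my assumption), the mean at a true 0.059 rises to 0.098 and average power falls to 68%.

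**Precision.** Inverting the noncentral F gives 95% intervals of 0 to 0.27 for an observed 0.059, 0 to 0.36 for 0.138, and 0.21 to 0.66 for 0.5. For an observed 0.138, the upper limit implies 3.92 × 0.637/0.363 = 6.9, so 7 per arm. The lower limit of 0 implies no finite n.

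**Sign.** At d = 0.2 the chance that a pilot favours placebo is Φ(−0.2√7.5) = Φ(−0.55), about 29%. Eta squared is positive in those pilots too.

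**Does correction help?** Epsilon squared, 1 − (1 − η²) × 29/28, averages 0.010, 0.057, 0.135, 0.197 and 0.500 for the five true values, so the bias is essentially gone. Omega squared is similar and slightly low. But epsilon squared is zero or negative, giving no usable n, in 61%, 34%, 12% and 4% of pilots for the first four rows. Among positive estimates average power is only 39%, 67%, 76% and 78%. Hedges' g multiplies d by 1 − 3/(4 × 28 − 1) = 0.973. Sizing from its absolute value lifts average power only from 70% to 73% at d = 0.5, and from 54% to 56% at d = 0.2.

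**The case against.** The strongest reply has three parts.

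First, a reader might infer that this plan will systematically undersize the next trial. Putting the expected value 0.090 into the formula gives 40 per arm where 63 are needed, with 61% power. The same step at η² = 0.010 gives 86 against 389, with 26% power. That is not what the plan describes. A pilot yields one value, not the mean over many pilots. Pilot by pilot, undersizing at d = 0.5 to 1.0 is close to a coin flip, gross oversizing is about as common as gross undersizing, and the mean planned n exceeds the need. This part stands: the loss is in average power, and only at d = 0.2 is undersizing clearly the usual outcome.

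Second, at the effects that the plan hypothesises the bias is negligible, and at 0.5 it leaves n unchanged. This also stands. But 0.5 and 0.8 mean d = 2 and d = 4, and a pilot run to estimate the effect cannot presume values of that size.

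Third, Section 9.2 says only that the estimate can be used, and arm means and SDs are reported, so direction and a corrected index are recoverable. That is fair, and it limits the harm. It does not supply an interval or change the advice in 9.2 and 9.5.

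A reader might also infer a selection effect. At a true 0.138, pilots reaching significance average 0.243, and one reaching 0.5 would imply about 4 per arm against 25. Section 2.2 says a large-scale study would follow a successful pilot, and 9.4.2 has its success threshold. No section joins the two into a rule for launching or sizing that study, so this inflation is conditional.

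**Conclusion.** The point holds in a limited form. The index that 9.2 and 9.5 offer for powering later trials is biased upward for small to moderate effects at 15 per arm (+53% at a true 0.059, +19% at 0.138), has no sign, and comes without an interval. Sizing a trial from it would give, on average, about 70–75% power for d of 0.5 to 1.0 and 54% for d = 0.2, against a target of 80%. These figures rest on 30 evaluable participants, equal arms, no covariate, normally distributed areas with equal variance, and an assumed next trial at two-sided 0.05 and 80% power.

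Imprecision matters more than bias, so correcting the point estimate alone would not make it a safe planning value. The documents do not support a claim that the next trial is bound to be too small. Nothing here affects the conduct or safety of the present study.

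**What to change.** In 9.2, 9.4 and 9.4.2, report the signed between-arm difference in mean VAS area, and a bias-corrected effect size (Hedges' g, or omega or epsilon squared) with its 95% confidence interval. Keep partial eta squared as a descriptive value. Bring 9.1 and the Protocol Summary into line, and say which index the success threshold in 9.4.2 then refers to.

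Reword 9.2 and 9.5 so that future sample sizes rest on a conservative limit of that interval, or on a minimum important difference in VAS area combined with the pilot SD, and not on the raw point estimate. Where the interval reaches zero, its lower limit gives no finite sample size and the second route is the workable one.

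The cost is SAP wording and a line or two of output, best settled before unblinding; no new data or participants are needed. The reported effect will be slightly smaller and visibly imprecise, and omega or epsilon squared may come out at zero or below.

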9.3 Analysis Datasets

Efficacy data will be analyzed for all subjects who received at least one dose of study-drug and provided at least one endpoint measurement during the non-blinded study phase. For the blinded study phase efficacy data will similarly be analyzed for all randomized patients providing at least one endpoint measurement. A separate per protocol patient population defined as patients providing complete efficacy data will also be defined for each study phase.

Safety and tolerability data will be analyzed for all enrolled patients receiving at least one dose of studydrug during the non-blinded study phase and then for all randomized participants during the blinded study phase.

9.4 Description of Statistical Methods

Data from this pilot study will be summarized separately for the non-blinded study phase and by study arm for the blinded study phases. The area under the VAS curve after subtracting baseline value will be determined using the linear trapezoidal method. These areas will be determined for the efficacy population using the last observation carried forward (LOCF). The mean and standard deviation for the non-blinded phase will be determined and the effect size for the mean area from zero calculated. For the blinded phase week 3 (after a 2 week "washout") will serve as the baseline and the area under the VAS curve from baseline will be calculated using LOCF imputation for missing post baseline data. To avoid potential cross-over effects from the 9 week non-blinded phase when all subjects receive active drug, after randomization, subjects will receive either active drug or placebo. The first 2 weeks of this 6 week period will be a washout period from statistical analysis. While subjects will still receive study drug, data collection for that phase will not begin until week 3 of that 6 week period. The mean and standard deviation in area under the VAS curve from baseline for each study arm will be determined and the partial eta effect size for the mean difference between study arms calculated. This summary will be performed for the per protocol study population as well to investigate the relative influence of missing data on the effect size determination.

Frequencies and percentages for the secondary safety and tolerability endpoints will be determined using the ITT patient population for the non-blinded study phase and all randomized participants during the nonblinded study phase. The other secondary endpoint, incidence of the change in THI of 1 point or greater, will be summarized by study arm for those participants providing at least 1 post-week 3 baseline THI measurement.

The analyses will be refined and adjusted in anticipation of study termination and data lock.

9.4.1 General Approach

The study design is a pilot, proof of concept, two-phase study. The first non-blinded study phase is to provide tolerability, regimen adherence, and initial safety data for the active treatment. The second phase after 2 week washout allows for efficacy comparison of the mean VAS difference from baseline between

active drug and placebo and incidence of THI changes greater than 1 point. Please see Schematic of Study Design.

9.4.2 Analysis of the Primary Efficacy Endpoint(s)

The primary efficacy endpoint is the area under the VAS curve from baseline for all randomized participants during the blinded study phase. The week 3 data after two week washout will serve as the baseline and the interval/ratio scaled area determined using the linear trapezoidal method. The expectation is that placebo participants' post-baseline VAS data will remain relatively consistent with baseline values while active treatment will trend post-baseline. Using an LOCF imputation strategy is therefore a conservative strategy for handling missing data by understating trending in the active treatment group without introducing trending in the placebo group. The mean and standard deviation by study arm in the area under the VAS curve from baseline will be presented along with the partial eta squared effect size estimate for the mean difference between study arms. The availability of data will be determined by study arm at each post-baseline study time point during the blinded study phase to investigate the potential influence of missing data. A per-protocol analysis will also be presented to further investigate the influence of missing data on the primary efficacy endpoint.

The area under the VAS curve from baseline will similarly be determined and analyzed separately for the open label/non-blinded study phase. Since this measure is biased by participant knowledge of treatment the effect size of the mean VAS area from baseline will be determined and cautiously interpreted.

As included in Section 9.1, the effect size will be calculated and interpreted using η^2 =0.2 as a small effect, η^2 =0.5 as a medium effect, and η^2 =0.8 as a large effect (20). These cut-offs will be used to judge the strength of the treatment relative to placebo control with medium ($\eta^2 \ge 0.5$) considered a treatment "success."

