4.2 Study Endpoints

4.2.1.1 Primary Study Endpoints

The primary outcome measurement will be the collective area under the Visual Analog Scale (VAS) curve above the week 3 baseline as assessed from week 3 to week 6 of the double blinded study phase.

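### The primary VAS area is measured from a baseline taken 2 to 3 weeks after randomisation, so any arm difference already present by then cancels out

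*Combined protocol and SAP*

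**What the plan says.** Sections 7.2.3.9 and 9.6.1.1 place randomisation, and the first supply of blinded drug, at Visit 11 (Week 9), after nine weeks of open-label oxytocin. For the blinded phase, Section 4.2.1.1 defines the primary endpoint as "the collective area under the Visual Analog Scale (VAS) curve above the week 3 baseline as assessed from week 3 to week 6". Section 9.2 computes it by the trapezoidal rule "after subtracting the baseline (week 3) VAS value from each subsequent measure", and Section 9.4.2 confirms: "The week 3 data after two week washout will serve as the baseline".

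Section 9.4 gives the reason: "To avoid potential cross-over effects from the 9 week non-blinded phase when all subjects receive active drug". It continues: "The first 2 weeks of this 6 week period will be a washout period from statistical analysis". The assigned drug or placebo is still taken during those two weeks, so this is a gap in the analysis and not a break in treatment.

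Section 9.4.2 expects that, on placebo, "post-baseline VAS data will remain relatively consistent with baseline values while active treatment will trend post-baseline". From this it concludes: "Using an LOCF imputation strategy is therefore a conservative strategy for handling missing data".

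**The concern.** A baseline should precede the treatment difference being measured. This one follows it by 2 to 3 weeks, so subtracting it removes whatever part of the treatment effect has already appeared. The carry-over argument supports leaving blinded weeks 1-2 out of the window. It does not support subtracting week 3. If the washout does its job, placebo patients have lost the drug effect by week 3, and that loss is what gets subtracted.

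The expected pattern of flat placebo and trending active is the one in which little is lost. It is possible: with 5 IU steps every two weeks, the top dose is first dispensed at Visit 9 (Week 7), about two weeks before randomisation. But the plan does not justify it for a design in which the placebo arm has just been taken off active drug.

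The source of the week-3 value is also undefined. Visit 14 (Week 12) lists only the TFI, the visit tables mark unspecified questionnaires, and the daily log could supply several candidate values.

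Section 9.5 makes the effect size for a future trial the main goal. If the drug works and symptoms return soon after the switch, the pilot would report an effect size close to its no-effect value, and the next trial would be planned on it.

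**Working it through.** The plan gives no figure to reproduce: n = 30 is stated without alpha, power, SD or target difference.

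**1. Timeline.** Randomisation is at Week 9. Blinded week 3 starts at 9 + 2 = Week 11 and ends at 9 + 3 = Week 12; the blinded phase ends at 9 + 6 = Week 15. Because the day is not defined, I take the baseline at *b* = 2 and at *b* = 3 weeks.

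**2. Cancellation (no assumptions).** Let D(t) be the placebo-minus-active mean VAS at t weeks after randomisation. The expected arm difference in the planned area is

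∫ from b to 6 of [D(t) − D(b)] dt = ∫ from b to 6 of D(t) dt − (6 − b)·D(b).

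For a constant 2-point difference from *b* = 3 onward: 2 × 3 − 3 × 2 = 0. Without the subtraction it is 6 point-weeks.

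**3. Gradual relapse (assumed curve).** Let D(t) = 2(1 − 2^(−t/h)), with half-time h. The 2 points are borrowed from the protocol's own dose-response threshold (Section 4.1).

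At h = 1 and b = 3, D(3) = 1.75. The area over weeks 3-6 is 5.68 and the part removed is 3 × 1.75 = 5.25. This leaves 0.43, or 8%. At b = 2 the figures are 7.32 − 4 × 1.50 = 1.32, or 18%. Weekly trapezoids give 0.42 of 5.67 and 1.30 of 7.30.

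| Half-time | Relapse already present at baseline (b = 2 / 3) | Area kept (b = 2 / 3) |
|---|---|---|
| 1 week | 75% / 88% | 18% / 8% |
| 2 weeks | 50% / 65% | 31% / 17% |
| 4 weeks | 29% / 40% | 40% / 24% |

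**4. Sensitivity.** Assumed: 15 per arm, SD 2, one VAS per week, no dropout. A two-sided 5% test is used as a yardstick only, since the plan has no test. The comparator is ANCOVA of mean VAS from b to 6 on Week 9 VAS.

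Worked case: exchangeable correlation 0.7, h = 1, b = 3.
- Planned area: weights (−2.5, 1, 1, 0.5); variance 4 × 0.3 × 8.5 = 10.2; SE √(2 × 10.2/15) = 1.17; noncentrality 0.42/1.17 = 0.36; power 6%.
- ANCOVA: mean difference 1.88; residual variance 4 × (0.7 + 0.3/4 − 0.49) = 1.14; SE √(2 × 1.14/15) = 0.39; noncentrality 4.8; power above 99%.

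Power over exchangeable correlation 0.5-0.85, planned area vs ANCOVA:

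| Pattern | b = 2 | b = 3 |
|---|---|---|
| All relapse, h = 1 week | 10-20% vs 98-100% | 6-8% vs 98-100% |
| All relapse, h = 2 weeks | 14-35% vs 88-100% | 8-15% vs 91-100% |
| All relapse, h = 4 weeks | 12-27% vs 56-88% | 8-15% vs 62-92% |
| Half relapse, h = 1 week | 6-9% vs 41-63% | 5-6% vs 42-64% |
| Active gains steadily from randomisation | 24-64% vs 83-99% | 16-42% vs 89-100% |
| Arms separate only after the baseline | 47-93% vs 59-90% | 49-94% vs 56-89% |

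Scanning h from 0.1 to 104 weeks within this curve, the planned area never exceeds 14-35% (b = 2) or 8-16% (b = 3). Under AR(1) correlation 0.7-0.95 the maxima are 12-40% and 8-22%. Rejection under no effect is about 5% for every method.

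**5. In the plan's own metric** (all relapse, h = 1, exchangeable), median partial eta squared for the planned area is 0.025-0.048 (b = 2) or 0.018-0.021 (b = 3). Under no effect it is 0.016-0.017. ANCOVA gives 0.39-0.59 and 0.39-0.60.

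**The case against.** The strongest objection concerns shape. Every relapse curve in step 3 is steepest at randomisation, so it always puts much of the separation before the baseline. If relapse starts only after a lag, the ranking can close or reverse. With a 2-week lag, then a 1-week half-time and b = 2, the planned area has 69-99% against 76-98% (exchangeable) and 62-100% against 58-88% (AR(1)). With a 3-week lag and b = 3, it is 58-98% against 61-92% and 58-100% against 41-70%. This stands: the documents give no symptom-return time, and the plasma half-life in the background section is not one. It is the late-separation pattern in the last table row, and the remedy has to cover it.

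Section 3 also lists comparisons it calls primary (Week 15 against Week 9, and a last-week comparison between arms) that do not subtract week 3. An early, lasting effect would show there. But Sections 4.2.1.1 and 9 define the primary analysis as the week-3 area, so these are competing definitions and do not repair it.

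It is also fair that the plan is descriptive, that power is not its metric, and that the comparison is unbiased under no effect. The eta-squared figures answer the first two points for one scenario only. The LOCF point is not quantified here, because the calculations assume no dropout.

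**Conclusion.** The concern holds. Cancellation of the week-3 arm difference is exact and needs no assumption. How much is lost depends on when the arms separate, which is unknown, and on assumed SD, correlation and effect size. If separation begins at randomisation, through relapse on placebo or continued gain on active, the planned area was less sensitive in every setting tabulated, often close to its no-effect value. If separation starts only after the baseline, the two approaches are comparable under exchangeable correlation, and the planned area is mostly better under AR(1) (48-99% against 37-65% at b = 3). This is a loss of sensitivity, not a source of false positives. It must still be fixed, because the pilot exists to estimate this effect size. The cut-off of eta squared 0.5 for success is a separate problem and is not relied on here.

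**What to change.** In Sections 4.2.1.1, 9.2, 9.4 and 9.4.2, replace the week-3 baseline with wording such as:

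> Baseline for the blinded phase is the mean of the last 7 daily-log VAS values before Visit 11 (Week 9). The primary endpoint is mean VAS (or AUC) over blinded weeks 3-6, compared between arms in all randomised participants by ANCOVA with Week 9 VAS as covariate. Partial eta squared for arm is reported with a 95% CI.

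- Keep the exclusion of blinded weeks 1-2.
- Keep the week-3-referenced area as a sensitivity analysis, and state which day and source supply the week-3 value.
- In Section 3, name the new definition as the single primary one. Make item 3 (last week, with Week 9 VAS as covariate) a named supportive analysis and item 2 descriptive. In the linear late-separation case the last-week ANCOVA has 85-100% power (exchangeable) or 74-97% (AR(1)).
- Delete the claim that LOCF is conservative; it rests on the same unsupported expectation.
- Section 9.4.2 already plans that "The availability of data will be determined by study arm at each post-baseline study time point during the blinded study phase". Add the number randomised per arm with no VAS in weeks 3-6.

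No new data are needed: the VAS log is reviewed at Visit 11 and the weeks 3-6 values are already used. The cost is an IRB-approved amendment (Section 12.2), with a record that the change was made without sight of unblinded results, and some sensitivity given up if separation is late.
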